8.1.3 Imputation of Missing Data

For individual daily pain scores, since a mean is used in the calculation of the primary endpoint, it is not necessary to replace values missing on random intermittent days; weeks will have average values as long as a single value for that week is present.

For the primary analysis, no missing values will be imputed; a sensitivity analysis may be performed using the following imputation algorithm:

Daily sleep diary data may be handled in an identical manner to the pain scores.

Continuous outcomes included in the list of key secondary outcomes that are collected in-clinic may be handled as above, minus the step of creating weekly averages of daily values and with steps being done by visit instead of week.

Patients with missing PGI-C at a given visit will be considered non-responders at that visit for the purposes of treatment comparisons; additional tabulations will summarize the number and

percentage in each category out of non-missing values as well as a count of the missing values. 30% and 50% responders will be handled similarly with missing values being imputed as non-responders.

No missing safety data will be imputed.

8.2 Efficacy Assessments

8.2.1 Weekly Average of Daily Worst Long COVID Pain Intensity Score

The daily eDiary is an important aspect of this study, and all patients must receive training explaining what is being asked of them, when to complete the diary, and how to use the diary system effectively. Patients will be trained on use of the diary system at Visit 1. Additionally, patients should complete the training on accurate pain reporting and placebo response reduction training as required.

During the 7-day run-in Phase (7 days immediately preceding Visit 2 [Baseline/Randomization Visit; Day 1]) patients will be asked to record their worst daily Long COVID pain intensity on the 11-point (0–10) NRS scale using 24-hour recall and to assess sleep quality from the previous evening, also using an 11-point NRS scale. The average of the 7 days immediately preceding Visit 2 (Baseline Randomization Visit; Day 1) will serve as the Baseline pre-treatment scores.

During the treatment phase, each evening, the system will prompt the patient to reflect on the past 24 hours and record their worst pain intensity, assess their sleep quality from the previous evening, and log study drug dosing from the previous night (post-randomization).

Patients will receive instructions and a password that uniquely identifies them when they log into the diary system, along with instructions about what to do if they have difficulty completing the diary.

The diary should be started the evening of Visit 1 and completed daily until Visit 6 (Week 14). Patients should be instructed to complete the diary in the evening before dosing. Once the patient has properly identified themselves, the diary will prompt answers to the following:

- Rate your worst Long COVID pain intensity during the last 24 hours on a scale from 0–10, where 0 is “no pain” and 10 is “pain as bad as you can imagine”. Rate your sleep quality last night on a scale from 0–10 where 0 is the “best possible sleep” and 10 is the “worst possible sleep”.

After randomization to study drug at Visit 2, the following questions will be added to the daily diary (starting in the evening of the day after randomization, Day 2):

- Did you take your study drug last night? (Yes/No)
- If yes, how many tablets of study drug did you take last night? (1 tablet/2 tablets)

These daily values will be averaged into a weekly mean; since a mean is used in the calculation of the primary endpoint, it is not necessary to replace values missing on random intermittent days.

As described above, the baseline pain score will be defined as the average of the pain scores from the 7 days prior to the baseline visit. Pain scores must be recorded on at least 5 out of the 7

days immediately preceding the baseline visit in order for the patient to qualify for randomization.

The mean of the daily, patient self-reported, 24-hour recall, pain severity scores for the 7 days of each week will serve as the pain score for that study week. All available values will be used; if a patient has at least one value for the week, the week is non-missing. Because there is a -4 day and +7 day window around the scheduling of Visit 6 (Day 99), the study weeks will be anchored by the timing and completeness of their final study visit. Ideally, patients appearing in-clinic on Day 99 (defining randomization as Day 1), would have last filled out their diary on Day 98; therefore, “Week 14” would include Days 92-98; the protocol-defined window allows visit 6 as early as Day 95, resulting in a nominal “Week 14” including Days 88-94. Likewise, patients may appear in-clinic per protocol as late as Day 106, resulting in a “Week 14” interval running from Day 99-105.

Due to impacts from the COVID-19 pandemic, the criteria for calculating the Week 14 average will be marginally relaxed beyond the protocol-specified visit windows to allow for additional flexibility by permitting data collected during Week 13 to be used to calculate the Week 14 average: working backwards from Day 98, the first non-missing day (as early as Day 91) will serve as the LAST day of Week 14 for the purpose of anchoring and any non-missing values in the 6 days prior to that day will contribute to the average. If a patient does not have a non-missing value on/after Day 91, any available data from Day 85-91 will be averaged as Week 14 and Day 91 will serve as the anchor. Patients without data on/after Day 85 will be missing for Week 14 and handled as described below. Specific examples of calculating the Week 14 pain score are described in [Appendix D](#).

Each week prior to Week 14 will be based on 7-day intervals; depending on the interval selected for “Week 14”, this will result in Week 1 having less than 7 days or some “extra” days prior to Week 1. Extra days will be dropped and not included in the analysis; in the case of less than 7 days, the available days will be averaged, as long as there are non-missing values. The earliest day included in the Week 1 average will be the data entered the day after randomization (covering roughly the 24 hours following their first dose of study drug).

For patients who withdraw from the study early, that do not have a final study visit or complete the study but do not have data in the 7 days preceding their last visit, the last day of diary data (at or prior to Day 106) will serve as the anchor point for dividing the available data into weeks. First, the nearest nominal end day for a weekly period is identified and this week will be the assigned the data from the 7 days immediately preceding the anchor date. For example, if a patient early terminates on study Day 24, the Week 3 (nominally ending on day 21) average will be based on the 7 days prior to Day 24 (Days 17-23). Lost to follow-up patients that continue to fill out the diary into Week 14 and beyond will have non-missing values for the Week 14 time point for diary outcomes (as well as any prior weeks for which data are present). Day 106 will be the last allowable day to be included in the average.

Week	Nominal Study Day Intervals
Baseline	Day -7 to -1

Day of Randomization	Day 1
Week 1	Day 2 to 7
Week 2	Day 8 to 14
Week 3	Day 15 to 21
Week 4	Day 22 to 28
Week 5	Day 29 to 35
Week 6	Day 36 to 42
Week 7	Day 43 to 49
Week 8	Day 50 to 56
Week 9	Day 57 to 63
Week 10	Day 64 to 70
Week 11	Day 71 to 77
Week 12	Day 78 to 84
Week 13	Day 85 to 91
Week 14	Day 92 to 98

Change from baseline will be defined as the pain score at each week minus the baseline pain score (with baseline and weekly pain scores derived as described above). Thus, negative changes will denote lesser pain and larger negative values will denote greater improvement.

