10. EFFICACY ANALYSES

10.1 Primary Efficacy Analysis

10.1.1 Estimand

Population

The analysis population will be patients with PASC as defined by the protocol inclusion/exclusion criteria.

Variable

The primary endpoint will be the change from baseline to Week 14 in the diary NRS weekly average of daily self-reported worst Long COVID pain intensity scores.

Intercurrent Events

For all intercurrent events, data will be analyzed as observed and missing data (both intermittent and following discontinuation) will be assumed to be missing at random. All patients that complete at least one diary pain entry will contribute to the model estimation.

Population-Level Summary

The population-level summary will be the difference in least-square means between treatment arms (analyzed as randomized) at Week 14 from the primary analysis model. See [Section 10.1.2](#) for details.

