12.3 Exposure and Compliance

The treatment duration will be calculated and summarized based primarily on CRF data for first and last dose dates (number of days=last dose date – first dose date+1). If these values are missing or patients' diary data indicate dates that exceed this period, the diary dates will be utilized.

Days of exposure will be based on patients' responses to the daily questions regarding medication usage. The number of days on study drug is the total number of days a patient responds that study drug was taken. If the CRF data for the last dose date is a date not included in the diary, it will be added to the count (this should be true for most completing patients since they do not fill out a diary the day of their last visit). The number of patients with total exposure by visit weeks (≤ 2 weeks, 2 to ≤ 4 , 4 to ≤ 8 , 8 to ≤ 12 , 12 to ≤ 14 and >14 weeks) will be presented. Missing days where the patient did not complete the diary will be treated as though study drug was not taken. Days of exposure will also be calculated for the days on each dose of study drug.

Additionally, the number and percentage of patients that drop back to one tablet per day will be summarized and the week in which they reduced their dose will be tabulated (among those that had a dose reduction).

Compliance will be similarly summarized across all study visits for each treatment arm. Study drug compliance as a percentage will be defined as the exposure days defined above divided by the total number of expected days on treatment multiplied by 100. The expected number of days will be the date of last diary recorded dose-randomization date +1. This compliance reporting

will take into account whether or not they took any medication, but will not account for the number of tablets they took on a given day.

Compliance will be summarized with descriptive statistics by treatment arm. The number and percentages of patients within certain categories of compliance (e.g. < 60%, 60% to < 80%, 80% to \leq 100%, greater than 100%) will also be presented.

A listing of drug accountability data based on CRF data will be provided.

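### For patients without a usable final visit, the SAP 8.2.1 anchor rule read literally omits the last diary score and conflicts with the rest of that section and with Appendix D

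*SAP*

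**What the plan says.** SAP Section 8.2.1 gives a rule for three groups: early withdrawers, patients with no final visit, and completers with no diary data in the 7 days before their last visit. For them, "the last day of diary data (at or prior to Day 106) will serve as the anchor point". The nearest nominal week end is found, and "this week will be the assigned the data from the 7 days immediately preceding the anchor date". The same paragraph adds three things:

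- A worked example: for early termination on Day 24, the Week 3 "average will be based on the 7 days prior to Day 24 (Days 17-23").
- An upper limit: "Day 106 will be the last allowable day to be included in the average".
- A statement that patients lost to follow-up who keep completing the diary into Week 14 have a non-missing Week 14 value.

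Other places describe the window differently. The relaxed Week 14 rule, earlier in Section 8.2.1, works back from Day 98. The first day found with an entry "will serve as the LAST day of Week 14 for the purpose of anchoring and any non-missing values in the 6 days prior" are averaged. That part also says a single value makes a week non-missing. A patient seen on Day 99 "would have last filled out their diary on Day 98; therefore, “Week 14” would include Days 92-98". Appendix D tabulates the Week 14 window by last available diary day. Section 12.3 remarks of most completers that their last dose date is not in the diary "since they do not fill out a diary the day of their last visit". Section 8.2.2 applies the same derivation to the sleep quality score.

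**The concern.** If the anchor is the last diary day and the week is the seven days before the anchor, the anchor day lies outside its own week. Two programmers working from the same SAP could then derive different weekly scores for the same patient, one from the rule and one from the example or Appendix D.

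The score left out is the one nearest to dropout. The primary analysis (SAP Section 10.1.2) uses no imputation and assumes data are missing at random, so a withdrawer's last observed weeks are what that patient contributes. Sleep quality, first in the key secondary test order (Section 8.1.1.2), inherits the same windows. Where the anchor day holds the only entry of a week, the question becomes whether the week has a value at all.

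**Working it through.** **Inputs.** A is the last diary day (anchor, Section 8.2.1). Nominal week ends are Days 7, 14, ..., 98 (table in Section 8.2.1). Two windows are compared:

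- Literal rule: Days A−7 to A−1.
- Inclusive rule (as in the relaxed Week 14 rule): Days A−6 to A.

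**1. The SAP's own example (stated: Week 3 = Days 17-23).**

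| Anchor | Literal | Inclusive |
|---|---|---|
| A = 23 (no entry on the termination day) | 16-22 | 17-23 |
| A = 24 (entry on Day 24, or termination day used as anchor) | 17-23 | 18-24 |

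Day 23 is nearest to Day 21 and Day 24 is also nearest to Day 21, so both fall in Week 3. If the diary stops the day before the visit, as the SAP describes for scheduled final visits, the literal rule does not reproduce the example and the inclusive rule does. If there is a Day 24 entry, the literal rule reproduces the example, and both discard that entry.

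**2. Upper limit.** The anchor is at most Day 106. The latest literal window is therefore 106−7 to 106−1, or Days 99-105. Day 106 can never enter the anchored week, although the same paragraph names it as the last day that may. This conflict needs no assumption about the diary.

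**3. Appendix D.** Sixteen rows give a specific last diary day (91 to 106, taking the 106+ row as 106).

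| Last diary day | Printed | Literal | Inclusive |
|---|---|---|---|
| 91 | 85-91 | 84-90 | 85-91 |
| 92 | 85-92 | 85-91 | 86-92 |
| 93 to 105 (13 rows; e.g. 98) | e.g. 92-98 | e.g. 91-97 | e.g. 92-98 |
| 106+ | 99-105 | 99-105 | 100-106 |

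The literal rule matches 1 of 16 rows (106+). The inclusive rule matches 14 of 16. The Day 92 row fits neither: it spans 92 − 85 + 1 = 8 days.

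**4. Same patient, two Week 14 windows.** Take no final visit and last diary Day 95. Day 95 is 3 days from Day 98 and 4 from Day 91, so the anchor rule also labels it Week 14. The relaxed Week 14 rule and Appendix D give Days 89-95; the literal anchor rule gives Days 88-94. The SAP does not say which governs.

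**5. Sole entry on the anchor day.** Take no final visit and a single late entry on Day 98. The literal window is Days 91-97 and is empty. The inclusive window is Days 92-98 and holds one value, which Section 8.2.1 says is enough.

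**6. Size per patient with a full diary.** The two windows share six days, so

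inclusive mean − literal mean = (score on Day A − score on Day A−7) / 7.

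A 1-point difference gives 1/7 = 0.14 points, 3 points give 3/7 = 0.43, and the scale maximum gives 10/7 = 1.43. Illustration with assumed scores (Days 16-21 = 5, Day 22 = 7, Day 23 = 8): literal (6×5 + 7)/7 = 37/7 = 5.29; inclusive (5×5 + 7 + 8)/7 = 40/7 = 5.71.

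**The case against.** The best defence is that the intent is clear. The Day 24 example gives Days 17-23, and if no diary is completed on the visit day that window keeps the last score. A programmer who follows the example loses nothing. This has force, but it leaves rule and example disagreeing, and the rule is what would be programmed. It also rests on a diary habit that the SAP states for scheduled visits and completers, not for early terminations. For the same reason, the conflict with the example is conditional.

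Several stronger readings are tempting and are not supported:

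- *That the primary endpoint score of every early withdrawer is wrong.* The primary endpoint is the Week 14 change. Patients with no data on or after Day 85 are missing at Week 14, so the anchor rule sets only their earlier weeks.
- *That the SAP makes Week 14 missing for a no-visit patient with one late entry.* The literal window would be empty, but the same paragraph says such patients are non-missing. The plan contradicts itself; it does not declare the week missing.
- *That a patient whose only post-baseline entry is Day 2 drops out of the model.* The literal window is Days −5 to 1, but Section 10.1.1 says "All patients that complete at least one diary pain entry will contribute to the model estimation", and Section 8.2.1 makes Day 2 the first day of Week 1. This is the same contradiction in a corner case.
- *That the result is biased.* The rule is the same in both arms. A direction appears only if one assumes pain moves in a particular way just before dropout.
- *That Appendix D is a clean standard.* Its 106+ row agrees with the literal rule and its Day 92 row agrees with neither.

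**Conclusion.** The point holds as a wording error in a stated derivation rule. As written, the anchor rule excludes the day it anchors on. That contradicts the relaxed Week 14 rule, 15 of 16 Appendix D rows and its own Day 106 limit. It also contradicts the worked example if no diary is completed on the termination day.

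For most early withdrawers the consequence is confined to weeks before Week 14, which bear on the Week 14 estimate only through the repeated-measures model. For no-visit patients with late diary data, the Week 14 window itself is ambiguous. The weekly mean moves by 0.14 points per 1-point difference between the dropped and the added score, and not at all when the two are equal. The documents give no dropout rate, no count of no-visit patients and no day-to-day variability, so the effect on the treatment difference cannot be computed. The point deserves correction before unblinding, but nothing shows that it would change the trial's conclusion.

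**What to change.** In SAP Section 8.2.1:

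1. Define the anchored week as the anchor date (last day of diary data) and the 6 days before it.
2. Restate the example by diary day: last diary entry on Day 23, so Week 3 = Days 17-23.
3. State that the same rule governs Week 14 for patients with no final visit.
4. Set one upper limit in the text and in the 106+ row of Appendix D. With Day 106 the row becomes Days 100-106. With Day 105 the printed Days 99-105 stand and the text changes.

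In Appendix D, correct the row for last diary Day 92 from the 8-day span 85-92 to 86-92.

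The sleep score follows automatically through Section 8.2.2. The cost is a few lines of SAP text and one programming check before unblinding. No additional data are needed and patients are not affected.

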8.2.2 Weekly Average of Daily Sleep Quality Score

The weekly average of daily sleep quality score will be obtained in the same manner as the weekly average of the daily worst long COVID pain intensity score, via electronic Interactive Response Technology (IRT) system. Derivation of the weekly average sleep quality scores and censoring of data will be treated the same as the weekly average pain scores described in [Section 8.2.1](#), using the same windows based on the date of collection. It should be noted that the sleep prompt asks about the prior night's sleep; thus, patients report their sleep starting the first night that they take randomized drug through the night between day 97-98, if their final visit is day 99. As with pain, negative changes will denote improvement in sleep quality and larger negative values will denote greater improvement.

8.2.3 Modified Michigan Body Map

The Michigan Body Map (MBM) is based on the 2011 FM Survey Criteria, a tool that is commonly used to assess for the presence of multi-site pain in fibromyalgia (FM), a disorder characterized by widespread body pain, along with comorbid symptomatology similar to that experienced by patients with Long COVID. The 2011 FM Survey Criteria include the assessment of pain in 19 specific body areas using the Widespread Pain Index (WPI). The areas from the WPI are then combined with the Symptom Severity scale to assess the presence and severity of FM. The MBM is a graphic mannequin with the 19 areas from the WPI superimposed upon it in anatomically relevant locations. The MBM also contains 16 additional areas for more general use. The MBM, and its online version, have been validated in patients with chronic pain.

Tonix Pharmaceuticals has modified the MBM (mMBM) in consultation with its authors. The

Two versions of the mMBM will be used in the study, the Screening version and the Baseline/Post-Randomization Version. The screening Version will assess a patient's eligibility to enter the study, based on the number of body regions with pain and the Baseline/Post-Randomization Version will be used for assessment of outcomes. The two versions are described in more detail below.

At screening

At screening (Visit 1), the patient will complete the “Screening Visit” version of the mMBM with a 3 month look-back period, which includes:

- [REDACTED]
- | [REDACTED]

Note: In order to be eligible for the study, the patient must have Long COVID pain in at least 4 out of 7 body regions on Part 2 of the screening mMBM.

At Baseline/Post-Randomization Visits (Visit 2-Visit 6)

At randomization through the end of the study, the patient will complete “Baseline/Post-Randomization” version of the mMBM with a 7-day look-back period, which includes:

- [REDACTED]
- | [REDACTED]
- | [REDACTED]
- | [REDACTED]

The region of pain that is selected as “most bothersome” at the Baseline Visit will be referred to as the “index site” thereafter. The “index site” will be followed from the Baseline Visit through V6 as a part of the exploratory analyses. Additional analyses related to the mMBM have been incorporated as exploratory endpoints as well. Refer to Appendix 2 of the Protocol for an exact

copy of the mMBM and definition of body regions.

The following endpoints will be derived using the mMBM:

- Change from Baseline in the total number (1-7) of the modified Michigan Body Map pain regions identified as having pain at each post-randomization clinic visit
- Change from Baseline in average NRS Long COVID pain intensity across the 7 pain regions in the modified Michigan Body Map at each post-randomization visit; regions without pain identified will be assigned a value of 0
- Change from Baseline in NRS Long COVID pain intensity within the index site region on the modified Michigan Body Map at each post-randomization visit
- Change from Baseline in NRS Long COVID pain intensity within the worst region for a given visit on the modified Michigan Body Map at each post-randomization visit; this will compare the value for the worst region at a visit and the worst region at baseline

8.2.4 Sheehan Disability Scale

SDS is a brief self-reporting tool that rates the extent to which work/school, social life, and home life or family responsibilities are impaired by the symptoms on a 10-point visual analog scale. The 3 items can also be summed into a single dimensional measure of global functional impairment that ranges from 0 (unimpaired) to 30 (highly impaired). If a patient is not working/in school for reasons unrelated to their disease state, that item is not completed; in this case, the average of the two other items will be imputed for this measure when calculating the total score (but not for reporting on that individual measure).

